**PROTOCOL SUMMARY**

Sponsor: Allergan Pharmaceuticals International Limited, [name]
	
Investigational Products: Juvéderm® VOLIFT™ with Lidocaine
	
Developmental Phase: Phase IV, Post-marketing

Title of Study: LIPS: Prospective, open-label study to evaluate the effectiveness of Juvéderm® VOLIFT™ with Lidocaine for lip augmentation
		

Protocol Number: CMO-MA-FAS-0512
		

Number of Subjects: 60 subjects
		

Indication: Lip augmentation
		

Primary Study Objective: To evaluate the effectiveness of Juvéderm® VOLIFT™ with Lidocaine for lip augmentation.
 
Secondary Study Objectives: To quantify the Investigators’ and subject’s assessment of aesthetic improvement of their lips.
		

Methodology: This is a prospective, open-label, multi-centre, interventional, medical device, post-marketing study. Each subject will act as his/her own control. Eligible subjects will undergo treatment with Juvéderm® VOLIFT™ with Lidocaine injected into the lips for lip augmentation.
 
All subjects will sign an informed consent form, and begin at the Screening Visit (V0). Filler treatment (Juvéderm® VOLIFT™ with Lidocaine) will be performed at V1 (Initial Treatment visit) and data will be collected at this visit for all relevant parameters as per the Schedule of Study Procedures, Treatments and Assessments (Table 1.1). Fourteen days after the initial treatment, subjects will return to the clinic and the Investigator will assess whether a Touch-up treatment is to be performed at this visit (V2). Follow-up visits will occur at V3, V4, V5, and V6 at 1, 3, 6, 12 months after the last treatment.
		

**Study Schema**

**Criteria for Evaluation:**

Primary Endpoint

The primary endpoint will be the responder rate for lip fullness on the Lip Fullness Scale (LFS2), which is defined as the proportion of subjects who show  $\geq 1$ -point improvement on the LFS2 compared to baseline assessment at Day 30 (after last treatment received) as assessed by the Investigator.

Secondary Endpoints

- Investigator assessment of oral commissures lines as measured by the 4-point Oral Commissures Severity Scale (OCSS) change in mean from baseline to V3, V4, V5, and V6.
- Subject’s assessment of overall satisfaction with lips as measured by the FACE-Q Lips Questionnaire change in mean from baseline to V3, V4, V5, and V6.
- Investigator’s assessment of global facial aesthetic improvement as measured by the 5-point Global Aesthetic Improvement Scale (GAIS) at V2, V3, V4, V5, and V6.

## Clinical Study Protocol: CMO-MA-FAS-0512

- Subject's assessment of global facial aesthetic improvement as measured by the 5-point GAIS at V3, V4, V5, and V6.
- Subject's assessment of natural look, feel and smoothness of their lips as measured on a 5-point Lickert scale after each treatment and at V3, V4, V5, and V6.
- Investigator's assessment of product smoothness as measured on a 5-point Lickert scale after each treatment and at V3, V4, V5, and V6.
- Investigator's assessment of dynamic lip lines upon animation at V3, V4, V5, and V6.

**Key Criteria for Inclusion:**

1. Male or female, 18 years of age or older
2. Signed the Institutional Independent Ethics Committee (IEC)-approved informed consent form prior to any study-related procedures being performed
3. Accept the obligation not to receive any other facial procedures or treatments anywhere in the lower face (below the orbital rim), neck, and oral cavity at any time during the study that are not related to the study
4. [REDACTED]
5. Women of childbearing potential must have a negative urine pregnancy test before each injectable treatment and practice a reliable method of contraception throughout the study
6. Ability to follow study instructions and likely to complete all required visits and assessments, as assessed by the Investigator.

[figure not shown]
**Key Criteria for Exclusion:**

[figure not shown]
1. [REDACTED]
2. Has lip tattoos or is planning lip tattoos during the course of the study, piercings, facial hair, or scars that would interfere with visualization of the lips and perioral area
3. Has dentures or any device covering all or part of the upper palate, and/or severe malocclusion or dentofacial or maxillofacial deformities
4. Has undergone oral surgery (e.g., tooth extraction, orthodontia, or implantation) within 6 weeks before enrollment or is planning to undergo any of these procedures during the study
5. Has ever undergone facial plastic surgery or received permanent facial implants (e.g., polymethylmethacrylate, silicone, polytetrafluoroethylene) anywhere in the face or neck, or is planning to be implanted with any of these products during the study

6. Has undergone semi-permanent dermal filler treatment (e.g., hyaluronic acid, calcium hydroxylapatite, poly-L-lactic acid) in the lower face (below the orbital rim) within 24 months before enrollment or is planning to undergo such treatment during the study
7. Has undergone mesotherapy or cosmetic resurfacing (laser, photo-modulation, intense pulsed light, radiofrequency, dermabrasion, chemical peel, or other ablative or non-ablative procedures) anywhere in the face or neck, or Botulinum toxin injections in the lower face (below the orbital rim) within 6 months before enrollment or is planning to undergo any of these procedures during the study
8. Has used any lip plumping products within 10 days before enrollment or is planning to use such products during the study (study treatment may be delayed as necessary to accommodate this 10-day washout period)
9. Has begun using any over-the-counter or prescription, oral or topical, anti-wrinkle products for the lips or around the mouth within 90 days before enrollment or is planning to begin using such products during the study (subjects who have been on a regimen of such products for at least 90 days are eligible for the study if they intend to continue their regimen throughout the study)
10. Is on an ongoing regimen of anti-coagulation therapy (e.g., warfarin) or non-steroidal anti-inflammatory drugs (NSAIDs) (e.g., aspirin, ibuprofen) or other substances known to increase coagulation time (e.g., herbal supplements with garlic or ginkgo) within 10 days of undergoing study device treatment (study treatment may be delayed as necessary to accommodate this 10-day washout period)
11. Is on a concurrent regimen of lidocaine or structurally related local anesthetics (e.g., bupivacaine)
12. Has a history of anaphylaxis, atopy, or allergy to lidocaine, hyaluronic acid (HA) products, or Streptococcal protein, or is planning to undergo desensitization therapy during the study
13. Has an active inflammation, infection, cancerous or precancerous lesion, or unhealed wound in the mouth area
14. Has porphyria
15. Has epilepsy
16. Has impaired cardiac conduction, severely impaired hepatic function, or severe renal dysfunction
17. Has any uncontrolled disease
18. Females who are pregnant, nursing, or planning a pregnancy
19. Current enrollment in an investigational drug or device study, participation in such a study within 6 weeks before enrollment, or be planning to participate in another investigation during the course of this study
20. Is an employee (or immediate relative of an employee) of the Investigator, Allergan, or a representative of Allergan

21.	

Products, Dose, and Mode of Administration:
 

 
Juvéderm® VOLIFT™ with Lidocaine is indicated for the treatment of deep skin depressions, face contouring, and volume restoration via deep dermis or lips mucosa injection.
 
The Investigator will determine the appropriate volume of Juvéderm® VOLIFT™ with Lidocaine to be injected to augment the lips It is anticipated that the volume of Juvéderm® VOLIFT™ with Lidocaine to be injected for lip augmentation [REDACTED]
	

Concomitant Medications:
 
Therapy considered necessary for the subject’s welfare may be given at the discretion of the Investigator, including but not limited to medications for other conditions (i.e., hypertension, diabetes, etc.), and treatment of adverse events (AEs).
 
All medications or treatments (including any dermal or facial aesthetic procedures) received by the subject within 30 days before the Initial Treatment visit and throughout the study, must be recorded in the study source documents and electronic case report form (eCRF).
	

Study Duration:
 
Each subject will participate in the study for up to approximately 6 months.
	

Statistical Methods:
 
The primary efficacy endpoint is the responder rate for lip fullness on the LFS2, which is defined as the proportion of subjects who show <math>\geq 1</math>-point improvement on the LFS2 at the Day 30 visit compared to baseline assessment, as determined by the Investigator at the clinic visit. As there is no formal statistical hypothesis testing in this study descriptive statistics will be provided only.
 
Details of the analyses for all other efficacy endpoints will be documented in the Statistical Analysis Plan (SAP).
	

■ [REDACTED]  
■ [REDACTED]  
■ [REDACTED]

**LIST OF ABBREVIATIONS**

Abbreviation	Definition
AE	adverse event
ADE	adverse device effect
CFR	Code of Federal Regulations
DFU	Directions For Use
eCRF	electronic case report form
FDA	Food and Drug Administration
GAIS	global aesthetic improvement scale
GCP	Good Clinical Practice
HA	hyaluronic acid
ICF	informed consent form
ICH	International Conference on Harmonisation
IEC	Independent Ethics Committee
IRB	Institutional Review Board
ISR	injection site reaction
LFS2	lip fullness scale
NSAIDs	non-steroidal anti-inflammatory drugs
OCSS	oral commissures severity scale
POLSS	perioral lines severity scale
SAE	serious adverse event
SADE	serious adverse device effect
UADE	unanticipated adverse device effect
US	United States

## 1 INTRODUCTION

### 1.1 BACKGROUND

As a key aesthetic feature of the face, fullness and voluptuousness of the lips are associated with attractiveness, sensuality, and youth. Similar to the skin, however, the lips are prone to intrinsic and extrinsic factors that can dramatically change their appearance over time.

Repetitive and underlying action of the orbicularis oris muscle leads to the formation of visible, fine, vertical rhytides surrounding the lips. The tolls of gravity coupled with the loss of lip volume and support cause the upper lip to lengthen and the lip to fall vertically. As collagen production diminishes, the Cupid's bow and vermilion border lose their distinction. The morphological changes of the lips over time become an obvious sign of aging. Unfortunately, because the connotation with youth is the ability to be an active and productive member of society, the pressure on individuals to conceal the signs of aging is tremendous. The inability to do so is correlated with increased anxiety and depression.

Treatment with temporary dermal fillers can provide volume to the lips and perioral area, three-dimensionally restoring the natural contour of the region to which it is applied and thereby reducing some of the signs of aging lips. Several technologies have been developed for cosmetic augmentation of the lips, including injection of paraffin, oils, silicone, polymethylmethacrylate beads, autologous fat, and injectable collagen. However, allergic reactions, inadequate duration effects, and logistics of the treatment (e.g., separate surgeries) have made them impractical. The development of cross-linked hyaluronic acid (HA)-based dermal fillers has since provided a safe, effective, and long-lasting option to volume enhancement of the lips. Currently, lip augmentation is recognized as one of the most common uses for dermal fillers, especially HA products.

Restoration of aging lips is an intricate endeavor in which the physician must take into account the multiple changes that have contributed to their overall aged appearance. The areas of injection for lip augmentation include the cutaneous (white) and red lips, i.e., vermilion (body of the red lip), vermilion borders (often in the potential space between the skin and the orbicularis oris muscle), Cupid's bow and philtral columns, perioral rhytides (vertical "lipstick" lines), and oral commissures (marionette folds). Injection into the vermilion and vermilion borders may indirectly cause improvement in perioral line severity. Treatment of the perioral lines and oral commissures may not be indicated in all patients, and treatment to accentuate the Cupid's bow and/or philtral columns may not be desired by many. Ideally, usage of a product with the malleability and range to treat different areas of the lips and perioral complex would provide the most realistic and satisfactory aesthetic result.

### 1.2 JUVÉDERM® PRODUCTS

As described below, the investigations assessing the safety and effectiveness of HA-based dermal fillers for volume restoration of the lips have demonstrated treatment success and high patient satisfaction. Longevity of treatment with HA fillers has been reported to be longer than treatment with collagen although the longevity of effect is relatively short-lived compared to treatment of other facial areas.

Clinical Study Protocol: CMO-MA-FAS-0512

---

- In a multi-center European post-marketing study of the safety and effectiveness of Juvéderm® VOLBELLA without lidocaine for lip enhancement, 60 subjects desiring lip enhancement and who met eligibility criteria were treated. Interim results 3 months post-treatment show that 93.2% of subjects displayed  $\geq 1$ -point improvement on the 4-point Lip Fullness Scale and 100% of Investigators and 98.3% of subjects affirmed that the pre-established lip fullness goal had been achieved (Study S15-002).
- In a multi-center clinical feasibility study for lip enhancement using Juvéderm® Ultra conducted in the United States (US) (Study JD-003), lip fullness and effectiveness of treatment was evaluated in 50 subjects who had established lip fullness goals. A separate, blinded Independent Evaluator and the subject assessed lip fullness, perioral lines, and oral commissures using validated scales. Standardized 3D images were taken to measure lip volume changes. Results showed that 71% of subjects ( $p < 0.0001$ ) achieved their lip fullness goals and improved  $\geq 1$ -point on the 4-point Lip Fullness Scale at the 12-week primary endpoint. Perioral line severity improved for up to 63% of subjects. Subject overall satisfaction at the 12-week endpoint was 82%, and 78% of subjects were willing or very willing to undergo study treatment again.
- A post-marketing surveillance study assessed treatment comfort and aesthetic effect in 57 patients treated with Juvéderm® Ultra Smile. The most common site for injection was the vermilion border, and 95% of injectors found the gel easy to inject. Furthermore, 99% of injectors rated improved aesthetic compared to baseline. Patient satisfaction with the product was 96%.

As with any dermal treatment injection, pain during administration is a possible side effect. Importantly, pain experienced during injection may compromise the physician's ability to perform the procedure with precision. Physicians typically use pain-relieving agents concomitant with injection, such as a nerve block, topical anesthesia, or a local anesthetic. The inclusion of lidocaine in the HA formulation itself is intended to reduce the patient's pain during the procedure and reduce or eliminate the need for additional pain-relieving agents. As described below, pain scores have consistently been reduced with HA-based dermal fillers containing a standard amount of lidocaine (0.3%) without compromising the aesthetic result. Furthermore, lidocaine in the formulation did not affect the rheology, duration of effect, or frequency of adverse events.

Juvéderm® VOLIFT™ with Lidocaine, included in the Juvéderm® range of products, is a malleable product capable of fitting the physical constraints that would be experienced with injection and volume expansion of the lips. The addition of lidocaine (0.3% w/w) is to increase patient comfort during treatment. Thus, the characteristics of Juvéderm® VOLIFT™ with Lidocaine should render it effective for lip volume restoration and enhancement, with increased patient comfort during treatment and a long-lasting duration.

The Juvéderm® family of non-animal HA gel implants was first CE marked and marketed in Europe in 2000, introduced into Canada in 2002, and US Food and Drug Administration (FDA)-approved in 2006. The Juvéderm® family is now approved in numerous countries throughout the world, including Korea (2004), Australia (2006), Mexico (2006), Brazil (2007), Columbia (2007), Hong Kong (2009), India (2009), and Taiwan (2009). Juvéderm®

Clinical Study Protocol: CMO-MA-FAS-0512

---

products have not been withdrawn from any country for any reason related to safety and effectiveness of the device.

Juvéderm® VOLIFT™ with Lidocaine gained CE mark in October 2011. The product label is as follows: medical devices for the treatment of cutaneous depressions and the restoration of volumes.

Refer to the *Juvéderm® VOLIFT™ with Lidocaine Directions for Use (Appendix 1)* for further details of the mitigation of risks of Juvéderm® VOLIFT™ with Lidocaine.

## **2 STUDY OBJECTIVES AND CLINICAL HYPOTHESIS**

### **2.1 STUDY OBJECTIVES**

#### **2.1.1 Primary Study Objective**

To evaluate the effectiveness of Juvéderm® VOLIFT™ with Lidocaine for lip augmentation.

#### **2.1.2 Secondary Study Objectives**

To quantify the Investigators' and subject's assessment of aesthetic improvement of their lips.

### **2.2 CLINICAL HYPOTHESIS**

The clinical hypothesis of this study is that a significant proportion of subjects treated with Juvéderm® VOLIFT™ with Lidocaine will achieve at least a 1-point improvement in the 5-point Lip Fullness Scale (LFS2) at 30 days post last treatment. Additionally, subjects will have a significantly higher satisfaction with lip appearance at post-treatment study visits when compared with baseline pre-treatment satisfaction scores, as measured by the mean change from baseline on the Satisfaction with Lips FACE-Q questionnaire. For subjects who additionally receive treatment for oral commissures a significant proportion of subjects will achieve an improvement in Oral Commissures Severity Scale (OCSS) score(s) at post-treatment study visits when compared with baseline pre-treatment scores. Investigators' and subjects' global satisfaction with the aesthetic outcome will also be assessed.

## **3 STUDY DESIGN**

[figure not shown]
This is a prospective, open-label, multi-centre, interventional, medical device, post-marketing study evaluating the effectiveness of Juvéderm® VOLIFT™ with Lidocaine for lip augmentation. Subjects will attend up to 7 visits: Screening, Initial Treatment, Day 14 (Touch-up, if required), Day 30, Month 3, Month 6, and Month 12. (Study Exit) (see *Figure 3.1*). 60 subjects will be enrolled.

Eligible subjects will undergo treatment with Juvéderm® VOLIFT™ with Lidocaine administered via injection for enhancement as per the current DFU. Fourteen days after the initial treatment, subjects will return to the clinic and the Investigator will assess the effectiveness of treatment. If the Investigator judges that optimum correction has not been achieved, an optional Touch-up treatment may be performed during the Day 14 visit.

Subjects who receive Touch-up treatment at the Day 14 visit will attend their Day 30 visit 30 days after their last treatment (ie, after Touch-up). Similarly, subsequent follow-up visits for those subjects who undergo Touch-up treatment will occur at 3 and 6, and 12 months after the last treatment received.

At 12 months the subject will return to clinic and carry out all assessments. If eligible for treatment as per the VOLIFT Directions For Use and have had no other treatments / medications as described in the Inclusion / Exclusion since 6 months, the subject will be offered a free retreatment injection of Juvéderm® VOLIFT™ with Lidocaine. If the decision is made to not retreat at 12 months, but a later retreatment is planned, then the subject can be treated outside the study with free treatment.

**Figure 3.1 Overall Study Design**

Note if touch-up treatment administered, V3, V4, V5, and V6 will be +14 days.

## 4 STUDY POPULATION AND ENTRY CRITERIA

### 4.1 NUMBER OF SUBJECTS

60 subjects will be treated in this study. Subjects who “drop out” after receiving treatment on Day 1 will not be replaced.

### 4.2 INCLUSION CRITERIA

The following are requirements for entry into the study.

1. Male or female, 18 years of age or older
2. Signed the Institutional Review Board (IRB)/Independent Ethics Committee (IEC)-approved informed consent form prior to any study-related procedures being performed

Clinical Study Protocol: CMO-MA-FAS-0512

---

3. Accept the obligation not to receive any other facial procedures or treatments anywhere in the lower face (below the orbital rim), neck, and oral cavity at any time during the study that are not related to the study
4. [REDACTED]
5. Women of childbearing potential must have a negative urine pregnancy test before each injectable treatment and practice a reliable method of contraception throughout the study
6. Ability to follow study instructions and likely to complete all required visits and assessments, as assessed by the Investigator.

### 4.3 EXCLUSION CRITERIA

1. [REDACTED]
2. Has lip tattoos or is planning lip tattoos during the course of the study, piercings, facial hair, or scars that would interfere with visualization of the lips and perioral area
3. Has dentures or any device covering all or part of the upper palate, and/or severe malocclusion or dentofacial or maxillofacial deformities
4. Has undergone oral surgery (e.g., tooth extraction, orthodontia, or implantation) within 6 weeks before enrollment or is planning to undergo any of these procedures during the study
5. Has ever undergone facial plastic surgery or received permanent facial implants (e.g., polymethylmethacrylate, silicone, polytetrafluoroethylene) anywhere in the face or neck, or is planning to be implanted with any of these products during the study
6. Has undergone semi-permanent dermal filler treatment (e.g., hyaluronic acid, calcium hydroxylapatite, poly-L-lactic acid) in the lower face (below the orbital rim) within 24 months before enrollment or is planning to undergo such treatment during the study
7. Has undergone mesotherapy or cosmetic resurfacing (laser, photo-modulation, intense pulsed light, radiofrequency, dermabrasion, chemical peel, or other ablative or non-ablative procedures) anywhere in the face or neck, or Botulinum toxin injections in the lower face (below the orbital rim) within 6 months before enrollment or is planning to undergo any of these procedures during the study
8. Has used any lip plumping products within 10 days before enrollment or is planning to use such products during the study (study treatment may be delayed as necessary to accommodate this 10-day washout period)
9. Has begun using any over-the-counter or prescription, oral or topical, anti-wrinkle products for the lips or around the mouth within 90 days before enrollment or is planning to begin using such products during the study (subjects who have been on a regimen of such products for at least 90 days are eligible for the study if they intend to continue their regimen throughout the study)
10. Is on an ongoing regimen of anti-coagulation therapy (e.g., warfarin) or non-steroidal anti-inflammatory drugs (NSAIDs) (e.g., aspirin, ibuprofen) or other substances known to increase coagulation time (e.g., herbal supplements with garlic or ginkgo) within 10 days of undergoing study device treatment (study treatment may be delayed as necessary to accommodate this 10-day washout period)

Clinical Study Protocol: CMO-MA-FAS-0512

---

11. Is on a concurrent regimen of lidocaine or structurally related local anesthetics (e.g., bupivacaine)
12. Has a history of anaphylaxis, atopy, or allergy to lidocaine, HA products, or Streptococcal protein, or is planning to undergo desensitization therapy during the study
13. Has an active inflammation, infection, cancerous or precancerous lesion, or unhealed wound in the mouth area
14. Has porphyria
15. Has epilepsy
16. Has impaired cardiac conduction, severely impaired hepatic function, or severe renal dysfunction
17. Has any uncontrolled disease
18. Females who are pregnant, nursing, or planning a pregnancy
19. Current enrollment in an investigational drug or device study, participation in such a study within 6 weeks before enrollment, or be planning to participate in another investigation during the course of this study
20. Is an employee (or immediate relative of an employee) of the Investigator, Allergan, or a representative of Allergan
21. 

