## 4.4 PERMISSIBLE AND PROHIBITED MEDICATIONS/TREATMENTS

### 4.4.1 Permissible Medications and/or Treatments

Therapy considered necessary for the subject's welfare may be given at the discretion of the Investigator, including but not limited to medications for other conditions (i.e., hypertension, diabetes, etc.), and treatment of adverse events (AEs). Medications should be taken consistently throughout the study and at the Investigator's discretion.

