## 6 STUDY VISIT SCHEDULE AND PROCEDURES

### 6.1 PATIENT ENTRY PROCEDURES

Prospective patients as defined by the criteria in *Sections 4.2 (Inclusion Criteria)* and *4.3 (Exclusion Criteria)* will be considered for entry into this study.

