#### 6.1.3 Washout of Prohibited Medications/Treatments

[figure not shown]
If washout of any medications is required, the subject must provide written informed consent before the washout can commence.

*Table 6.1* lists the medications/treatments that are prohibited during the study and the length of time that must pass between the medication/treatment and treatment in the study.

For additional information/examples of specific treatment/procedures, refer to *Section 4.3 (Exclusion Criteria)*.

Study treatment may be delayed as necessary to accommodate the washout period. If treatment is delayed beyond the 14-day screening period (see *Table 1.1: Schedule of Study Procedures, Treatments, and Assessments*), screening procedures are to be repeated as necessary to confirm participation eligibility. The inclusion/exclusion criteria must be reassessed and the patient eligibility confirmed prior to study treatment.

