**CONTRA-INDICATIONS**

- Do not inject *Juvéderm® VOLIFT™ with Lidocaine* in the periorbital area (eyelids, under-eye area, crow's feet) and glabellar region.
- Do not inject into the blood vessels (intravascular).
- Do not overcorrect.
- *Juvéderm® VOLIFT™ with Lidocaine* must not be used in:
  - Patients suffering from untreated epilepsy;
  - Patients who tend to develop hypertrophic scarring;
  - Patients with known hypersensitivity to hyaluronic acid;
  - Patients with known hypersensitivity to lidocaine or to amide-type local anaesthetics;
  - Patients suffering from porphyria;
  - Women who are pregnant or breastfeeding;
  - Children.
- *Juvéderm® VOLIFT™ with Lidocaine* must not be used in areas presenting cutaneous inflammatory and/or infectious processes (acne, herpes, etc.).

• *Juvéderm® VOLIFT™ with Lidocaine* should not be used simultaneously with laser treatment, deep chemical peels or dermabrasion. For surface peels, it is recommended not to inject the product if the inflammatory reaction generated is significant.

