- The combination of **Juvéderm® VOLIFT™ with Lidocaine** with certain drugs that reduce or inhibit hepatic metabolism (cimetidine, beta-blockers, etc.) is inadvisable.

- **Juvéderm® VOLIFT™ with Lidocaine** should be used with caution in patients showing symptoms of cardiac conduction disorders.

- Please recommend that the patient not use any makeup during the 12 hours following the injection treatment and that any extended exposure to the sun, UV rays and temperatures below 0°C be avoided, as well as any sauna or hammam sessions during the two weeks following the injection treatment.

- If the needle is blocked, do not increase the pressure on the plunger rod but stop the injection and replace the needle.

- Athletes should be made aware that this product contains an active principle that may produce a positive result in anti-doping tests.

- Medical practitioners must take into account the fact that this product contains lidocaine.

- The composition of this product is compatible with fields used for magnetic resonance imaging.

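### Exclusion 12 names allergy to lidocaine only, while the appended Directions for Use contraindicate hypersensitivity to the whole amide class of local anaesthetics; the two texts need to be reconciled

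*Protocol*

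**What the plan says.** **Allergy.** Exclusion 12 in Protocol section 4.3 reads "Has a history of anaphylaxis, atopy, or allergy to lidocaine, HA products, or Streptococcal protein". The Protocol Summary and SAP section 3.4.2 name the same allergens. The contraindications in Appendix 1 state that the product must not be used in, among others, "Patients with known hypersensitivity to lidocaine or to amide-type local anaesthetics".

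**Related anaesthetics.** Exclusion 11, one line above exclusion 12, applies to a subject who "Is on a concurrent regimen of lidocaine or structurally related local anesthetics (e.g., bupivacaine").

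**Medication.** Section 4.4.1 leaves therapy needed for the subject's welfare to the Investigator, "including but not limited to medications for other conditions (i.e., hypertension, diabetes, etc.)". Under its precautions for use, the DFU says that combining the product with "certain drugs that reduce or inhibit hepatic metabolism (cimetidine, beta-blockers, etc.) is inadvisable".

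**Which text decides entry.** Section 6.1 considers for entry "Prospective patients as defined by the criteria in" sections 4.2 and 4.3. Section 6.1.3 requires those criteria to be reassessed if treatment is delayed beyond the screening period. Section 3 says that treatment is given according to the current DFU, and section 11.4 says that products are used as licensed. For the optional Month 12 retreatment, section 3 adds an explicit eligibility condition: "If eligible for treatment as per the VOLIFT Directions For Use".

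**The concern.** Sites screen against the numbered criteria. If a criterion covers less than the contraindication it corresponds to, a subject can satisfy the list and still be someone for whom the manufacturer says the product must not be used. The gel contains lidocaine by design, so an allergy to anaesthetics of the same class bears directly on the product. What is at stake is subject safety and the clarity of the eligibility check, not the estimate of the responder rate.

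The drafting of exclusion 11 makes the gap easier to see. The protocol already extends from lidocaine to related anaesthetics when it considers current use, but it does not do so in the next line when it considers allergy.

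**Working it through.** No statistical quantity is involved, so the check is a comparison of texts.

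| Topic | Protocol (readable text) | DFU, Appendix 1 | Match? |
|---|---|---|---|
| Allergy to lidocaine | Excluded (item 12) | Contraindicated | Yes |
| Allergy to other amide-type anaesthetics | Not named in item 12 | Contraindicated | No |
| Current use of related anaesthetics | Excluded (item 11) | Not a listed contraindication | Different topic; does not close the gap |
| Drugs inhibiting hepatic metabolism | Section 4.4.1 allows medication for other conditions, with hypertension as an example | Inadvisable (precaution) | Not aligned, but not a contraindication |

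**Step 1: who falls in the gap.** Item 12 can be read as excluding any history of anaphylaxis or any atopy, whatever the cause. That reading favours the protocol, and I use it. The remaining subject must then have (a) a known hypersensitivity to an amide-type anaesthetic other than lidocaine, (b) no anaphylaxis, (c) no atopy, and (d) no known allergy to lidocaine, hyaluronic acid products or Streptococcal protein. Such a subject meets none of the readable allergy terms and does meet the DFU contraindication. If anaphylaxis and atopy count only when linked to the listed substances, the gap is wider.

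**Step 2: does item 11 catch this subject?** No. It asks whether the subject is taking a related anaesthetic now. A person allergic to one would not be expected to be on it.

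**Step 3: exposure.** The DFU composition gives 3 mg lidocaine hydrochloride per 1 mL. Section 5.3 anticipates at most 3.0 mL per patient. So 3 mg/mL × 3.0 mL = 9 mg at the anticipated maximum volume. This shows only that every treated subject receives lidocaine.

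**Step 4: which check applies at each injection.** Entry rests on sections 4.2 and 4.3. An eligibility condition that names the DFU is readable only for the Month 12 retreatment. For Day 1, section 3 says that treatment follows the DFU but states no separate DFU eligibility check in readable text, and none is readable for Day 14. On the readable text, the subject in Step 1 would meet the amide contraindication as an explicit eligibility question for the first time at Month 12.

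**Step 5: medication.** Section 4.4.1 names a condition, hypertension, and not a drug. The DFU precaution names beta-blockers and cimetidine. No readable passage connects the two. Section 6.1.3 says that Table 6.1 "lists the medications/treatments that are prohibited during the study", but its content cannot be read.

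**The case against.** The strongest reply is that the DFU is part of the protocol. It is Appendix 1. Section 3 ties treatment to it, section 1.2 refers to it for the mitigation of risks, section 5.3 refers to it for injection details, and section 11.4 says that products are used within their licence. An Investigator who injected a subject with a contraindication would depart from section 3. This stands. A reader might infer that the protocol authorises such an injection, or that only the Month 12 retreatment is tied to the DFU; the documents support neither. What remains is that the general promise to follow the DFU and the specific entry list disagree on one allergy, and the entry list is the operative screen.

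Second, exclusion 1 and inclusion 4 are redacted, exclusion 21 is blank, and Table 6.1 and much of the screening and pre-treatment procedure cannot be read. Any of these may bear on the point. This also stands, and it limits the claim to the readable criteria. It does not change the fact that the allergy criterion itself differs from the contraindication.

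Third, the protocol is not looser in general. It excludes all epilepsy where the DFU contraindicates only untreated epilepsy. It excludes impaired cardiac conduction where the DFU advises caution, and it excludes ongoing anticoagulant or NSAID regimens where the DFU asks for a warning. This is correct, so the point is confined to the passages cited.

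Fourth, a reader might infer that the DFU rules out users of beta-blockers or cimetidine. It does not: the text is a precaution, and discretion under section 4.4.1 can coexist with it. The medication point is therefore secondary.

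**Conclusion.** The allergy mismatch holds. Exclusion 12, in protocol and SAP alike, is narrower than the DFU contraindication by one class of allergens, and exclusion 11 does not make up the difference. Section 4.4.1 and the DFU precaution on hepatic metabolism are not cross-referenced in readable text; that is a lesser point of consistency.

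The documents give no prevalence of amide hypersensitivity or of the drugs concerned, so no count among the 60 subjects is offered. Given the conditions in Step 1, the group is probably very small. The reason to act is that the item is a contraindication.

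There is no shown effect on the results. It might be inferred that an affected subject would go unflagged and remain in the Per Protocol Set. The documents do not establish this: treatment outside the DFU departs from Protocol section 3 and could be recorded as a deviation, the sponsor reviews deviations to assign that set (SAP sections 5.5 and 5.6), and the set is only supportive because the primary analysis uses the Evaluable Set.

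The conclusion assumes that the redacted items do not already cover amide hypersensitivity. If one does, the remaining task is to make exclusion 12 agree with it.

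**What to change.** - Reconcile exclusion 12 in Protocol section 4.3, the Protocol Summary and SAP section 3.4.2 with the contraindications in Appendix 1.
- Check section 4.4.1, together with Table 6.1, against the DFU precaution on drugs that inhibit hepatic metabolism, and add a cross-reference if none exists in the unreadable text.
- Carry the reconciled text into the eligibility check before the Day 1 and Day 14 injections, so that these injections and the Month 12 retreatment are judged against the same list.

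The clinical wording belongs to the sponsor's medical lead; this point does not say which text should prevail. The cost is a wording amendment to the protocol, the matching SAP text, and an update of the eligibility check. Any effect on screen failures depends on how the texts are reconciled and cannot be sized from the documents. No analysis, table or sample-size statement needs to change.
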